regardless of treatment delays until radiographic disease progression per RECIST v1.1, initiation of a new anti-cancer therapy, withdrawal of consent, death, or study termination by the Sponsor, whichever occurs first. Thus, tumor assessments are to continue according to the schedule in participants who discontinue treatment for reasons other than disease progression or loss of clinical benefit. For participants who continue treatment after progressive disease, tumor assessments are to continue according to schedule until study treatment is discontinued. At the Investigator's discretion, tumor assessments may be repeated at any time if progressive disease is suspected.

Response will be assessed according to RECIST v1.1. Objective response at a single time-point will be determined by the Investigator according to RECIST v1.1. All primary imaging data used for tumor assessments may be collected by the Sponsor; centralized, blinded independent review of response endpoints by an independent review facility may be conducted.

The primary comparison of interest are the hazard ratio of OS of each experimental arm compared to nivolumab, assessing the superiority of the experimental arms over the active comparator treatment. The primary comparison of OS will be made regardless of whether participants withdraw from treatment or receive new anti-cancer therapy prior to disease progression. In order not to confound the OS endpoint, crossover from any of the treatment arms to another arm will not be allowed.

During the study, participants will be asked to complete patient-reported outcome (PRO) questionnaires at the beginning of the study, during study treatment, at treatment discontinuation, and during survival follow-up. These will assess disease and treatment-related symptoms, as well as functioning and overall health-related quality of life.

During the study, serum samples will be collected to monitor RO7121661, RO7247669, and nivolumab pharmacokinetics (PK) and to detect the presence of antibodies to RO7121661, RO7247669, or nivolumab. Blood samples for PK analysis may be collected at the participant's

home. This specifically applies to days where no other hospital assessments are required—i.e., C1D8 and C5D8.

Participant samples, including archival and fresh tumor tissue, serum, plasma, and blood samples, will also be collected for biomarker assessments.

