3. OBJECTIVES AND ENDPOINTS

The primary objective is expressed in the estimand framework through the 5 attributes as described in [Table 4](#).

Table 4 Estimands

Attribute	Study Definitions
Population	Patients with unresectable advanced or recurrent ESCC who are refractory or intolerant to one prior line of chemotherapy
Primary endpoint (variable)	Overall survival
Treatments	
 Experimental: 2100 mg Q2W RO7121661 Experimental: 2100 mg Q2W RO7247669 Active comparator: 240 mg Q2W nivolumab
Intercurrent events and their handling	New anti-cancer therapy and treatment discontinuation, handled via treatment policy (intercurrent event is ignored)
Summary measure	Hazard ratios

The objectives and corresponding endpoints are provided in [Table 5](#).

Table 5 Objectives and Endpoints

Objectives	Endpoints
Primary	
To evaluate the efficacy of RO7247669 compared with nivolumab.	
 OS, defined as the time from randomization to death from any cause
Secondary	
To evaluate the safety and tolerability of RO7121661 and RO7247669 compared with nivolumab.	
 Nature, frequency, and severity of adverse events (AEs) graded according to the National Cancer Institute (NCI) Common Terminology Criteria for Adverse Events (CTCAE) v5.0
To evaluate the efficacy of RO7247669 compared with nivolumab.	
 Objective response rate (ORR), defined as the proportion of participants with an objective response (i.e., complete response [CR] or partial response [PR]), according to RECIST v1.1 Disease control rate (DCR), defined as ORR + stable disease rate (SDR) Duration of response (DoR) for participants with ORR, defined as the time from the first occurrence of a documented objective response to disease progression according to RECIST v1.1 or death from any cause, whichever occurs first Progression-free survival (PFS) defined as the time from randomization to the first occurrence of progression as determined by the Investigator according to RECIST v1.1 or death during the treatment period or within 60 days of the last tumor assessment after treatment discontinuation from any cause, whichever occurs first Proportion of participants reporting clinically meaningful improvement in global health status/quality of life, emotional functioning, social functioning and dysphagia

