	as measured by the European Organisation for Research and Treatment of Cancer (EORTC) Quality-of-life questionnaire (QLQ)-C30, IL97, and OES-18, defined as an improvement of at least 10 points
To investigate the pharmacokinetics (PK) of RO7247669 and nivolumab.	
 Serum concentrations, PK profiles and parameters for RO7121661, RO7247669, and nivolumab
To evaluate the immune response after administration of RO7247669 and nivolumab.	
 Incidence and titer of RO7121661, RO7247669 or nivolumab anti-drug antibodies (ADAs) during the study relative to the prevalence of ADA at baseline
To assess treatment-induced pharmacodynamic changes (PD Biomarkers) in peripheral blood and tumor microenvironment	
 Changes from baseline in the phenotype and activation status (CD4/CD8 HLA-DR+Ki67+) of T-cell subsets in the peripheral blood Changes from baseline such as CD8 T-cell infiltration, proliferation (CD8+Ki67+) in the tumor microenvironment
To assess baseline characteristics in the tumor microenvironment as predictive biomarkers of response	
 Baseline PDL1, CD8+PD1+, CD8+TIM3+, and CD8+LAG3+ expression in the tumor microenvironment
Exploratory	
To evaluate the efficacy of RO7121661 and RO7247669 compared with nivolumab.	
 Changes in disease-related symptoms, function, and health-related quality of life as measured by the EORTC QLQ-C30, IL-97, and OES-18 Proportion of responses on the PGI-CI and PGI-S
To evaluate the efficacy of RO7121661 compared with nivolumab.	
 OS, defined as the time from randomization to death from any cause ORR, DCR, DoR, PFS as defined above according to RECIST v1.1 Proportion of participants reporting clinically meaningful improvement in global health status/quality of life, emotional functioning, social functioning and dysphagia as measured by the EORTC QLQ-C30, IL97, and OES-18, defined as an improvement of at least 10 points
To investigate the PK of RO7121661	
 Serum concentrations, PK profiles and parameters for RO7121661.
To evaluate the immune response after administration of RO7121661	
 Incidence and titer of RO7121661 ADAs during the study relative to the prevalence of ADA at baseline

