In the experimental arms, participants will receive RO7121661 or RO7247669 at a fixed dose of 2100 mg administered by IV infusion Q2W on Day 1 of each 14-day cycle (Section 6.1).

In the active comparator arm, participants will receive nivolumab at a fixed dose of 240 mg administered by IV infusion Q2W on Day 1 of each 14-day cycle (Section 6.1).

Treatment may be continued as long as participants are experiencing clinical benefit, as assessed by the Investigator, in the absence of unacceptable toxicity or symptomatic deterioration attributed to disease progression after an integrated assessment of radiographic data, biopsy results (if available), and clinical status for a maximum of

24 months. Participants who meet the criteria for disease progression per RECIST v1.1 will be permitted to continue study treatment if they meet all criteria for treatment beyond progression (Section 7.1.1).

regardless of treatment delays until radiographic disease progression per RECIST v1.1, initiation of a new anti-cancer therapy, withdrawal of consent, death, or study termination by the Sponsor, whichever occurs first (Section 8.1.1). Thus, tumor assessments are to continue according to the schedule in participants who discontinue treatment for reasons other than disease progression or loss of clinical benefit. For participants who continue treatment after progressive disease, tumor assessments are to continue according to schedule until study treatment is discontinued. At the Investigator's discretion, tumor assessments may be repeated at any time if progressive disease is suspected.

Response will be assessed according to RECIST v1.1 (Appendix 6). Objective response at a single time-point will be determined by the Investigator according to RECIST v1.1. All primary imaging data used for tumor assessments may be collected by the Sponsor; centralized, blinded independent review of response endpoints by an independent review facility may be conducted.

The primary comparison of interest are the hazard ratio of OS of each experimental arm compared to nivolumab, assessing the superiority of the experimental arms over the active comparator treatment. The primary comparison of OS will be made regardless of whether participants withdraw from treatment or receive new anti-cancer therapy prior to disease progression. In order not to confound the OS endpoint, crossover from any of the treatment arms to another arm will not be allowed.

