5.2 EXCLUSION CRITERIA

Participants are excluded from the study if any of the following criteria apply:

General Exclusion Criteria

1. Pregnancy, lactation, or breastfeeding.
2. Known hypersensitivity to any of the components of RO7121661, RO7247669, or nivolumab, including but not limited to, hypersensitivity to Chinese hamster ovary cell products or other recombinant human or humanized antibodies.

Medical Conditions

3. Patients with significant malnutrition. Patients whose nutrition has been well controlled for ≥ 28 days prior to randomization may be enrolled.
4. Evidence of complete esophageal obstruction not amenable to treatment.
5. Higher risk of bleeding or fistula caused by esophageal lesions invading adjacent organs (aorta or tracheobronchial tree). *Patients with manageable fistula may be included at the Investigator's discretion.*
6. Symptomatic central nervous system (CNS) metastases. Patients with previously treated brain metastases may participate provided they:
 - Are stable (without evidence of progression by computed tomography (CT) or magnetic resonance imaging (MRI) for at least 28 days prior to randomization).
 - Have no evidence of new or enlarging brain metastases for at least 28 days prior to randomization.
 - Are off systemic steroids for at least 28 days prior to randomization.
7. Spinal cord compression not definitively treated with surgery and/or radiation or without evidence that disease has been clinically stable for ≥ 14 days prior to randomization.
8. Active or history of carcinomatous meningitis/leptomeningeal disease.
9. Asymptomatic CNS primary tumors or metastases if they have requirement for steroids or enzyme-inducing anticonvulsants in the last 28 days prior to randomization.
10. Uncontrolled tumor-related pain. Participants requiring pain medication must be on a stable regimen at study entry.
11. Patients with an active second malignancy. Concurrent malignancy exceptions include: curatively treated carcinoma in situ of the cervix, good-prognosis ductal carcinoma in situ of the breast, basal- or squamous-cell skin cancer, Stage I melanoma, or low-grade, early-stage localized prostate cancer and any previously treated early stage non-hematological malignancy that has been in remission for at least two years.

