9.3.2 Efficacy Analyses

The efficacy analyses will include all participants in the ITT population, with participants grouped according to the treatment assigned at randomization (Table 9).

Descriptive statistics for the various endpoints will be provided for all 3 arms. However, since the primary aim has shifted from comparing the 2 experimental arms to nivolumab to only compare the RO7247669 arm to nivolumab, the statistical models will only include participants assigned to RO7247669 and nivolumab.

Table 9 Efficacy Statistical Analysis Methods

Endpoint	Statistical Analysis Methods
Primary	
OS
 
OS is defined as the time from randomization to death from any cause. Data for participants who are alive at the time of the data cutoff will be censored at the last date they were known to be alive. Data from participants without post-baseline information will be censored at the date of randomization.
 
Kaplan-Meier methods will be used to estimate median OS for each treatment arm and the 95% CIs for median OS will be computed using the Brookmeyer and Crowley method. The stratified Cox proportional hazard model will be used to estimate the hazard ratio for RO7247669 versus nivolumab (i.e., the magnitude of the treatment effect) and the corresponding 95% confidence interval, stratified by the protocol-defined stratification factors.

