Secondary	
ORR and DCR based on RECIST
 
ORR is defined as the proportion of participants who have achieved an objective response, characterized by a CR or PR according to RECIST v1.1. Objective response will be evaluated by treatment arm, and participants without post-baseline overall response assessments will be counted as non-responders. DCR is defined as ORR + stable disease rate (SDR).
 
An estimate of ORR for each treatment group as well as of the difference between the ORR of each experimental arm compared with the active comparator will be computed along with its 95% CI. The Mantel-Haenszel test will be used to compare the ORR of RO7247669 and the active comparator at the two-sided significance level of 20%, stratified by the protocol-defined stratification factors.
 
PFS based on RECIST
 
PFS defined as the time from randomization to the first occurrence of progression as determined by the Investigator according to RECIST v1.1 or death during the treatment period or within on study (i.e., within 60 days of the last study treatment tumor assessment) after treatment discontinuation, whichever occurs first. Participants who have not experienced disease progression at the time of analysis and who have not died during the treatment period or within 60 days of the last tumor assessment after treatment discontinuation will be censored at the time of the last tumor assessment. Participants with no post-baseline tumor assessment will be censored at the date of randomization.
 
The requirement that participants without a radiographic disease progression per RECIST v1.1 are still followed for the tumor assessments until progression or when the participant starts a new anti-cancer therapy (whatever occurs first), means that:

Endpoint	Statistical Analysis Methods

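### Synopsis, Section 4.1 and Table 4 still count the closed RO7121661 arm in the primary OS comparison, and no readable text limits its remaining contrasts to concurrent nivolumab participants

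*Combined protocol and SAP*

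**What the plan says.** Three places keep the three-arm primary comparison.

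- Section 4.1 (Overall Design): the primary comparison is the "hazard ratio of OS of each experimental arm compared to nivolumab, assessing the superiority of the experimental arms over the active comparator treatment".
- Section 1.1 (Synopsis): "The primary comparison of interest are the hazard ratio of OS of each experimental arm compared to nivolumab".
- Section 3, Table 4: the table is introduced with "The primary objective is expressed in the estimand framework through the 5 attributes as described in" Table 4. Its treatment attribute includes "Experimental: 2100 mg Q2W RO7121661", and its summary measure is in the plural.

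The rest of version 3 takes a narrower view. The only primary objective in Table 5 is RO7247669 versus nivolumab. The same table puts this among the exploratory objectives: "To evaluate the efficacy of RO7121661 compared with nivolumab". Section 4.1.4, the introduction to Section 9, Section 9.1 and the OS row of Table 9 all name RO7247669 only. Section 9.3.2 says that the primary aim has moved to that single comparison, that all three arms get descriptive statistics, and that "the statistical models will only include participants assigned to RO7247669 and nivolumab".

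Some RO7121661 contrasts survive. The ORR row of Table 9 plans the "difference between the ORR of each experimental arm compared with the active comparator" with a 95% CI, and the patient-reported-outcome row does the same for proportions improved. Safety of RO7121661 against nivolumab is still a secondary objective in Table 5. Section 9.2 defines the ITT set as everyone randomised and the safety set as everyone randomised who received any study treatment. Sections 4.1 and 6.3.1 continue randomisation to nivolumab after RO7121661 closes.

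**The concern.** Table 4 is where the primary question is formally defined, and it does not match the analysis meant to answer it. Someone working from Table 4 or Section 4.1 would expect two primary hazard ratios; someone working from Section 9 would produce one. That should be settled before unblinded results exist, and Section 9.4 gives sponsor study personnel full access to unblinded data at the interim analysis.

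The second issue is who serves as the control for RO7121661. Nivolumab participants who enter after closure could not have been assigned RO7121661. Including them makes the contrast partly non-randomised, so differences over calendar time or in case mix can pass for a drug effect. Exclusion criterion 5 was widened in the same version, with an added sentence beginning "Patients with manageable fistula may be included at the Investigator". Follow-up can also differ: the core analysis is triggered by OS events in the other two arms, and RO7121661 participants all entered before closure.

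**Working it through.** **Step 1. Scope of the primary OS comparison.**

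| Place in version 3 | Arms compared with nivolumab for primary OS |
|---|---|
| Section 1.1 Synopsis, design text | Each experimental arm |
| Section 4.1 | Each experimental arm, superiority |
| Table 4, treatments | RO7121661 and RO7247669 |
| Table 5, primary objective | RO7247669 only |
| Section 4.1.4 | RO7247669 only |
| Section 9, introduction | RO7247669 only |
| Section 9.1 | RO7247669 only, purpose stated as estimation |
| Section 9.3.2 and Table 9, OS row | RO7247669 only |

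Both sides are readable, current text. The conflict does not depend on the amendment rationale or on anything redacted.

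**Step 2. What is still computed for RO7121661.** Section 9.3.2 removes the arm from the statistical models, so no modelled OS or PFS hazard ratio is planned for it. The Mantel-Haenszel test of ORR is also limited to RO7247669. What remains is the ORR difference, the patient-reported differences, descriptive efficacy summaries set beside nivolumab, and safety tables by arm.

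**Step 3. Which nivolumab participants enter.** Efficacy uses the whole ITT set grouped by assigned arm. Safety uses all treated participants. Neither definition mentions the randomisation period, so as written participants from both periods are included.

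**Step 4. Size, as an illustration only.** The plan has no figure to reproduce here. Section 9.1 gives 255 as the former three-arm total, but the allocation ratio, the re-estimated size and the enrolment at closure are redacted.

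Let s be the share of nivolumab participants randomised after closure and d their ORR minus that of concurrent nivolumab participants. The pooled difference equals the concurrent difference minus s × d. With assumed s of 0.3 to 0.7 and d of 5 to 10 points:

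| | d = 5 points | d = 10 points |
|---|---|---|
| s = 0.3 | 0.3 × 5 = 1.5 | 0.3 × 10 = 3.0 |
| s = 0.7 | 0.7 × 5 = 3.5 | 0.7 × 10 = 7.0 |

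The sign is opposite to that of d, and with d = 0 there is no bias.

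For crude adverse-event proportions, assume a true rate of 0.06 per month in both arms, 6 months of exposure for RO7121661 and half of nivolumab, and 2.5 months for the other half of nivolumab.

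- RO7121661: 1 − exp(−0.06 × 6) = 0.302.
- Nivolumab: 0.5 × 0.302 + 0.5 × [1 − exp(−0.06 × 2.5)] = 0.5 × 0.302 + 0.5 × 0.139 = 0.221.

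Two equally safe drugs would then show about 30% and 22%.

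**Step 5. Price of restricting the control.** Assume equal allocation before closure, n per arm, and similar response rates. Total nivolumab is n/(1 − s). The variance of the difference is proportional to 1/n + (1 − s)/n with all nivolumab participants and to 2/n with concurrent ones only. The ratio of interval widths is √[2/(2 − s)]: √(2/1.7) = 1.08 at s = 0.3 and √(2/1.3) = 1.24 at s = 0.7. The interval is about 8% to 24% wider.

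**The case against.** The strongest reply is that Section 9.3.2 already settles the matter. It says outright that the aim has shifted, and every passage that specifies the OS analysis follows it. The three discordant places are then leftover three-arm text. This largely stands: the intended primary analysis is clear. It does not make the estimand table correct.

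A reader might infer that two primary tests are live and that the false-positive rate is inflated. The documents do not support that. Only one OS model is to be fitted, the readable OS row gives a hazard ratio and confidence interval without a test level, and the 20% level is stated for ORR and only for RO7247669. A reader might also expect a biased OS hazard ratio for RO7121661, but none is planned.

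On the control group, the reply is that no passage says later nivolumab participants will be used. That is fair: it follows from general set definitions and from silence. The separate technical document named in Section 9.3 was not available for this review and may contain a restriction. The amendment could also suggest a broad change in population. The rationale describes the change to inclusion criterion 4 as one of clarity, and exclusion criterion 5 gained one discretionary sentence, so no material shift is shown.

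Section 9.3.3 already calls for drug exposure, including duration, to be summarised, which would help a reader of the safety tables.

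**Conclusion.** The inconsistency is established by the text alone and needs no assumption. Version 3 defines the primary OS comparison in two ways, and the estimand table is on the wrong side of the plan's own stated shift in aim. It does not alter the RO7247669 analysis, and the documents do not support reading RO7121661 as a second primary result.

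The control-group point holds in a conditional form: as the analysis sets are written, the surviving RO7121661 contrasts include non-concurrent nivolumab participants, and no readable passage prevents it. Whether this causes bias depends on the non-concurrent share and on drift, neither of which can be read from the documents. The 1.5 to 7 points for ORR and the 30% versus 22% for adverse events show scale under assumed inputs; they are not estimates for this trial.

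Both parts should be fixed. Neither threatens the primary analysis.

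**What to change.** 1. In the synopsis and Section 4.1, name RO7247669 alone in both the hazard-ratio clause and the superiority clause.
2. In Table 4, remove RO7121661 from the treatments and make the summary measure a single hazard ratio.
3. In the ORR and patient-reported rows of Table 9, label the RO7121661 differences exploratory, in line with Table 5.
4. State in Section 9.3 that every RO7121661-versus-nivolumab contrast, safety included, uses only nivolumab participants randomised while the RO7121661 arm was open. If the separate technical document already says so, a cross-reference is enough.
5. Optionally, show exposure-adjusted adverse-event rates beside the crude proportions.

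The cost is a few words of protocol text and one flag for randomisation before or after closure. The only statistical loss is wider intervals for RO7121661 contrasts. The primary RO7247669 analysis, its population and its event trigger stay as they are.
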